### 3.2 Ineligibility Criteria

- 3.21 Patients who do not have available tissue for immunohistochemistry and nucleic acids analyses.
- 3.22 Patients who have received prior immunotherapy for unresectable or metastatic disease.
- 3.23 Patients with evidence of active brain metastases, or active leptomeningeal disease are ineligible. Patients with a history of brain metastases must have completed treatment (i.e. surgery or radiation) prior to enrollment..
- 3.24 Patients with inadequate tissue for analysis.

## 4.0 **REGISTRATION PROCEDURES**

All patients must be registered with the Georgetown CRMO (Clinical Research Management Office) before enrollment to study. Prior to registration, eligibility criteria must be confirmed with the Georgetown University Multi-Site Study Coordinator.

All study documents will be redacted by the local site to remove Protected Health Information as defined by HIPAA, and will be labeled with subject initials and number. These materials will be uploaded by the local site to a secure password-protected cloud-based Georgetown Box portal. Access to Box will be provided by Georgetown-LCCC staff, who will receive and review the source documents and confirm eligibility. The local site will receive written notification from Georgetown-LCCC regarding eligibility.

To register a patient, the patient registration form should be completed by the research nurse or data manager and faxed or emailed to the Coordinating Center Attn: Multi- Site coordinator: fax- [REDACTED] along with the source documentation for the eligibility review.

## 5.0 **STUDY DESIGN**

### 5.1 Protocol Summary

Eligible patients will receive treatment with nivolumab in combination with ipilimumab followed by nivolumab monotherapy following the FDA approved schedule. Patients will have a diagnosis of mucosal or acral lentiginous melanoma confirmed by a pathologist at each participating institution. Baseline unstained tumor slides will be collected. Some patient will have optional fresh biopsies at week#6. Pretreatment blood will be drawn, Peripheral blood mononuclear cells (PBMCs), and serum,will be separated.. Stool will be collected at baseline and at

3 weeks into treatment. All tissues, peripheral blood, and stool samples will be stored separately in frozen storage units within the MRFBC Virtual Tissue Repository until shipped to GU-LCCC.

## 5.2 Duration of Therapy and Response Assessment

All patients will receive nivolumab administered IV combined with ipilimumab administered IV every 3 weeks for 4 treatment cycles per standard of care (Induction) then continue with nivolumab administered IV per standard of care until progression, intolerable toxicity, or a maximum of 48 doses, whichever comes first (Maintenance). Patients exhibiting complete response (CR) should continue nivolumab monotherapy at least 12 weeks beyond documentation of CR, if possible. Patients will be treated within participating sites within the MRFBC. Commercial drugs will be used in this protocol and will not be supplied by the study.

Patients will be evaluated for response at approximately 12 weeks following the initiation of treatment and then approximately every 12 weeks. Response will be evaluated by the study investigators using the Response Evaluation Criteria in Solid Tumors (RECIST) criteria ,v1.1. (See appendix C). Following completion of therapy, patients with evidence of SD, PR or CR will have CT scans every 3 months for 2 years, then every 6 months during year 3 and then yearly thereafter for years 4 and 5. Attention will be paid to the time of disease progression. Both responding and non-responding patients will be followed until death.

## 6.0 **PATIENT MONITORING AND DATA SAFETY MONITORING**

As this is a tissue collection protocol in patients receiving standard of care therapy, patient management will occur through the standard operating procedures of the individual participating institution in general accordance with the FDA approved regimen.

Case Report forms documenting 1) patient demographic and tumor characteristics, 2) extent of treatment, 3) SAEs, 4) efficacy parameters and 5) specimen collection forms will be filled out for each patient.

The Principal Investigator and the Co-Investigators will discuss accrual, unusual toxicities and any other protocol issues including safety monitoring at their regular institution-based disease group meetings and on monthly investigator teleconferences. organized by the MRFBC.,

The Georgetown Lombardi Comprehensive Cancer Center will be responsible for the data and safety monitoring of this multi-site trial. As this study is an investigator initiated study utilizing FDA approved drugs for which the PI does not hold the IND it is

considered a moderate risk study which requires real-time monitoring by the PI and study team and semi-annual reviews by the LCCC Data and Safety Monitoring Committee (DSMC)

All Severe Adverse Events (SAEs) are required to be reported to the Multi-Site Coordinator Office at G-LCCC for review by the DSMC. (see below)

In addition, all SAEs are required to be reported to the local IRB per IRB policy. Based on SAEs, the IRB retains the authority to suspend further accrual pending more detailed reporting and/or modifications to further reduce risk and maximize the safety of participating patients.

Additionally, all SAEs will be reported to BMS Worldwide Safety using BMS SAE forms. Please refer to additional details in Appendix E. The sponsor/investigators are required to reconcile SAEs reported in the clinical database with SAE cases transmitted to BMS Global Pharmacovigilance (GPV&E); [REDACTED]. BMS requests this to be done quarterly and prior to the database lock or final data summary. A summary of the process for the sponsor/investigator is listed below:

- Sponsor/Investigator sends a request to BMS GPV&E for a “GPV&E reconciliation report”. Requests for reconciliation should be sent to [REDACTED]. The request should provide the BMS protocol ID, study title and PI, and sponsor/investigator protocol ID.
- BMS will send a report back to the sponsor/investigator. The data elements listed on the GPV&E reconciliation report will contain information the investigator can use for individual case identification. Cases on the list from BMS GPV&E should be compared to the SAE cases in the clinical database.

If the sponsor/investigator determines a SAE case was not transmitted to BMS GPV&E, the case should be sent immediately to BMS

Progress on the trial and the toxicities experienced will be reviewed by the G-LCCC Data and Safety Monitoring Committee every 6 months from the time the first patient is enrolled on the study. Results of the DSMC meetings will be forwarded to the G-LCCC IRB with recommendations regarding need for study closure.

A written copy of the DSMC recommendations will be given to the trial PI and the Georgetown IRB. If the DSMC recommends a study change for patient safety or efficacy reasons the trial PI must act to implement the change as expeditiously as possible. In the unlikely event that the trial PI does not concur with the DSMC recommendations, then the G-LCCC Associate Director (AD) of Clinical Research must be informed of the reason for the disagreement. The trial PI, DSMC Chair, and the LCCC AD for Clinical Research will be responsible for reaching a mutually acceptable decision about the study and providing details of that decision to the IRB. Confidentiality must be preserved during these discussions. However, in some cases, relevant data may be shared with

other selected trial investigators and staff to seek advice to assist in reaching a mutually acceptable decision.

If a recommendation is made to change a trial for reasons other than patient safety or efficacy, the DSMC will provide an adequate rationale for its decision. If the DSMC recommends that the trial be closed for any reason, the recommendation will be reviewed by the Associate Director for Clinical Research at G-LCCC. Authority to close a trial for safety reasons lies with the IRB, with the above described input from DSMC and the AD for Clinical Research.

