### 10.3.3 Toxicity

The toxicity of nivolumab in combination with ipilimumab is well established in the melanoma patient population (9-11). As this treatment represents standard of care for this patient population, a formal analysis of toxicity is not considered as an endpoint for this study. As such, only the incidence of severe adverse events (immune related AEs) will be collected at the end of each patient's treatment course. A single page form will be provided to collect this summary

information. (see Section 7).

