Appendix E.  
Bristol-Myer Squibb Worldwide Safety Adverse Event Reporting

All Serious Adverse Events (SAEs) that occur following the subject's written consent to participate in the study through 100 days of discontinuation of dosing must be reported to BMS Worldwide Safety

If the BMS safety address is not included in the protocol document (e.g. multicenter studies where events are reported centrally), the procedure for safety reporting must be reviewed/approved by the BMS Protocol Manager. Procedures for such reporting must be reviewed and approved by BMS prior to study activation.

The BMS SAE form should be used to report SAEs. If the BMS form cannot be used, another acceptable form (i.e CIOMS or Medwatch) must be reviewed and approved by BMS. The BMS protocol ID number must be included on whatever form is submitted by the Sponsor/Investigators.

Following the subject's written consent to participate in the study, all SAEs, whether related or not related to study drug, are collected, including those thought to be associated with protocol-specified procedures. The investigator should report any SAE occurring after these time periods that is believed to be related to study drug or protocol-specified procedure.

For studies with long-term follow-up periods in which safety data are being reported, include the timing of SAE collection

- In accordance with local regulations, BMS will notify investigators of all reported SAEs that are suspected (related to the investigational product) and unexpected (i.e., not previously described in the IB). In the European Union (EU), an event meeting these criteria is termed a Suspected, Unexpected Serious Adverse Reaction (SUSAR). Investigator notification of these events will be in the form of an expedited safety report (ESR).
  - Other important findings which may be reported by the as an ESR include: increased frequency of a clinically significant expected SAE, an SAE considered associated with study procedures that could modify the conduct of the study, lack of efficacy that poses significant hazard to study subjects, clinically significant safety finding from a nonclinical (eg, animal) study, important safety recommendations from a study data monitoring committee, or sponsor decision to end or temporarily halt a clinical study for safety reasons.
  - Upon receiving an ESR from BMS, the investigator must review and retain the ESR with the IB. Where required by local regulations or when there is a central

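### SAE means severe in Section 6 but serious in Appendix E, so a serious, non-severe event could reach BMS without reaching the DSMC

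*Combined protocol and SAP*

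**What the plan says.** Section 6.0 sets three reporting lines. For the coordinating centre and DSMC: "All Severe Adverse Events (SAEs) are required to be reported to the Multi-Site Coordinator Office at G-LCCC for review by the DSMC". For the IRB: "all SAEs are required to be reported to the local IRB per IRB policy". For the company: "all SAEs will be reported to BMS Worldwide Safety using BMS SAE forms", with a pointer to Appendix E for details. It also lists SAEs among the items documented on case report forms, and requires the sponsor/investigator to "reconcile SAEs reported in the clinical database with SAE cases transmitted to BMS Global Pharmacovigilance", quarterly and before database lock.

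Appendix E expands the abbreviation differently. It opens with "All Serious Adverse Events (SAEs) that occur following" the patient's written consent, and extends the duty "through 100 days of discontinuation of dosing must be reported to BMS Worldwide Safety". It covers events whether or not they are attributed to study drug and sets a 24-hour deadline.

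Two sections on data collection use severity language. Section 10.3.3 says that "only the incidence of severe adverse events (immune related AEs) will be collected", at the end of each patient's treatment course, on a single-page form. Section 11.0 describes a toxicity form for SAEs of Grade 3 and 4 together with immune-related events of Grade 2 to 4.

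The available text lists no seriousness criteria and does not say which meaning of SAE governs.

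**The concern.** In ordinary trial usage, severity is the intensity of an event, usually graded, and seriousness is its consequence for the patient. A high-grade laboratory abnormality may be severe without being serious; a moderate event may be serious because of what it leads to. Neither set contains the other. The protocol attaches one abbreviation to both and makes it the trigger for safety reporting.

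The recipients matter. Under Section 6.0 the IRB can suspend accrual on the basis of SAEs, and authority to close the trial for safety lies with it. The DSMC makes recommendations that the principal investigator must act on or formally dispute. Section 7.0 says that formal documentation of toxicity evaluation and management is not needed, so SAE reports are a main safety channel. A loose trigger could leave those bodies with a less complete picture than the company has.

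**Working it through.** No sample size, power or event count enters this point, so the check is a comparison of the text.

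**Step 1: what each section calls the event.**

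| Place | Term used | Scope and timing | Recipient |
|---|---|---|---|
| 6.0, first sentence on SAEs | Severe (SAE) | all | coordinating centre, for DSMC |
| 6.0, next sentence | SAE, not re-expanded | all, subject to IRB policy | local IRB |
| 6.0, next paragraph | SAE, not re-expanded | all, details in Appendix E | BMS |
| Appendix E | Serious (SAE) | related or not; consent to 100 days after dosing stops; within 24 hours | BMS |
| 10.3.3 | severe, glossed as immune-related | only these; end of treatment course | summary form |
| 11.0 | SAE of Grade 3 and 4; immune-related of Grade 2 to 4 | within 12 weeks of the decision to stop treatment | data capture system |

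**Step 2: trace each type of event.** Read *severe* wherever Section 6.0 says SAE, and *serious* wherever Appendix E does.

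| Event | DSMC (6.0) | IRB (6.0) | BMS (6.0 or Appendix E) |
|---|---|---|---|
| Severe and serious | yes | yes | yes, under both |
| Severe, not serious | yes | yes | yes, under 6.0 |
| Serious, not severe | **not required** | **not required by 6.0; depends on IRB policy** | yes, under Appendix E |
| Neither | no | no | no |

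Only the third row produces a difference between recipients.

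**Step 3: does the toxicity form catch the third row?** The documents do not tie *severe* to a grade. If it is taken as Grade 3 or 4, as the Section 11.0 form suggests, a serious Grade 2 event has a line on that form only if it is immune-related. Under 10.3.3 it is not collected at all, because that section is restricted to severe immune-related events.

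**Step 4: does reconciliation catch it?** Section 6.0 has the BMS list compared with SAE cases in the clinical database. The only action stated is to send BMS a case that it lacks; Appendix E likewise sends to BMS what had not been reported there. A case known to BMS but absent from the database would show up in the comparison, but no text then routes it to the coordinating centre, DSMC or IRB. What those bodies received is not part of the comparison.

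**Step 5: size.** The size would be the number of serious events that are not severe. The documents give no rate for these, so no figure can be derived.

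**The case against.** The strongest reply is that Section 6.0 describes one set of events sent to three places. It uses SAE without distinction for the DSMC, IRB and BMS and points to Appendix E. The natural inference is that *serious* was meant throughout and one word is wrong. This is at least as plausible as the literal reading, and it is why the consequence must be stated as *could*. It does not remove the defect: the wrong word sits in the operative sentence, and Sections 10.3.3 and 11.0 lean the same way.

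Other parts of the reply also stand. The DSMC reviews toxicity every six months, and that review is not limited to SAEs. IRB reporting follows a policy that is not in the documents. Section 10.3.3 concerns a summary where toxicity is not an endpoint, and is not itself a reporting trigger. Full reporting of serious events to BMS is unambiguous.

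A reader might go further in ways that the documents do not support:

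- *The bodies would receive different sets.* This holds only if sites apply Section 6.0 literally.
- *A severe, non-serious event reaches the DSMC and IRB but not BMS.* Section 6.0 uses the same term in its BMS sentence, so on the literal reading the event goes to BMS too.
- *Mismatches are built into the reconciliation.* That assumes the database follows the severity meaning; Section 6.0 says only that case report forms record SAEs.
- *The DSMC can close the study.* It recommends; authority to close for safety lies with the IRB.
- *The 54% and 55% Grade 3-4 rates cited in Section 1.6 give the size.* They are the proportions of patients in other trials with high-grade events, not events on which the two meanings disagree.

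**Conclusion.** Wrong as written, minor. The protocol contradicts itself on what an SAE is, in an operative safety rule. The consequence that survives runs in one direction: a serious event that is not severe could go to BMS without being required to go to the DSMC, might not go to the IRB depending on its policy, and may be left off the toxicity form. The stated reconciliation would not repair this.

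This rests on two assumptions: that some sites follow the wording of Sections 6.0, 10.3.3 and 11.0 literally, and that reports to BMS do not routinely pass through the coordinating centre, which the documents do not settle. The extent cannot be calculated from the documents. The objective response rate analysis is not affected.

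**What to change.** 1. In Section 6.0, replace *Severe* with *Serious* in the expansion of SAE.
2. State one definition of SAE, with its seriousness criteria written out, and apply it to the coordinating centre, DSMC, IRB, case report form and BMS. A cross-reference to Appendix E is not enough, because the appendix expands the term and sets scope and timing without giving criteria.
3. In Sections 10.3.3 and 11.0, state that all serious events are collected as they occur under Appendix E. Describe the end-of-treatment summary of graded or immune-related events as additional, and do not call its entries SAEs.
4. If the DSMC is also to see severe events that are not serious, list them separately by grade.

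Once the database and the BMS list share a definition, the reconciliation compares like with like. The cost is a short wording amendment, a notice to sites, and a few more reports to the coordinating centre, all of which Appendix E already requires for BMS.

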## **7.0 EVALUATION AND MANAGEMENT OF TOXICITY**

As this is a tissue collection protocol in patients receiving standard of care therapy, formal documentation of physician evaluation and management of toxicity is not necessary. However, it is suggested that patients with life-threatening or persistent, severe toxic reactions to either checkpoint inhibitors receive no further treatment with either agent.

## **8.0 CRITERIA FOR REMOVAL FROM STUDY**

As this is a tissue collection protocol, there is no specific criteria for removal from the study with one notable exception; if the patient withdraws consent. Otherwise, patients will continue to be followed clinically and information such as date of progression and date of death will be documented.

## **9.0 LABORATORY STUDIES**

The goal of this protocol are to acquire pretreatment tissue and blood from patients receiving standard of care nivolumab/ipilimumab combination for advanced MCM or ALM. Studies will be performed on both blood and tissue samples. Samples will be processed and stored at the Virtual Tissue Repository at each site for later batch shipping to the specified lab for analysis. Please refer to the Laboratory Manual in Appendix H for a complete instructions for specimen collection, processing, and storage. The tissue, blood and stool specimen shipment form can be found in Appendices A and B.

9.1 The materials required for this protocol are:

### Reports and Forms Required

- MRFBC Pathology Material Submission Form
- A copy of the surgical pathology report.

### Biological Material Submission

1. Available hematoxillin and eosin stained slides for pathology review
2. Tumor tissues from a primary melanoma excisional biopsy specimen or from a metastatic lesion
  - a. A paraffin-fixed, formalin-embedded tumor block, or
  - b. 16 unstained slides at 10micron and 10 unstained slides at 5 micron
3. Blood samples (see Section 9.3)
4. Stool samples (see Section 9.4)
5. (Optional) On-treatment fresh tumor biopsies at baseline and at 6-8 weeks of therapy

**NOTE:** An informed consent MUST be signed prior to the submission of any material for any correlative study, including mandatory diagnostic reviews.

**NOTE:** Appendix A and B must be submitted with each specimen submission at the end of the study. All samples, sample treatments, and collection time points are to be indicated on the form(s). Appendix A and B should accompany the samples to the central laboratory. Appendix C must be submitted with on-treatment biopsy specimens.

## 9.2 Studies to be performed on tissue

All participants will have either formalin-fixed, paraffin embedded (FFPE) tissue or fresh tumor biopsy collected at baseline. Fresh tumor biopsies will be obtained from safely accessible locations. Preferred biopsies include excisional or punch biopsy; 14-16 gauge core needle biopsies are acceptable if these are not feasible.

Please refer to Laboratory Manual for detailed instructions on specimen collection, processing, storage and shipment.

Baseline tumor specimen from each patient will be divided for three different biomarker analyses  
 (i) Tumor Whole Exome Sequencing (WES) for analysis of mutational burden, mutational pattern, prediction of tumor neoantigen peptides that react to patient's Major Histocompatibility (MHC) class I molecules requires 8 unstained slides at 10microns thickness. (ii) Immunohistochemistry study and quantification of immune cells and PD-L1+ cells infiltration at the invasive tumor margin requires 10 unstained slides at 5 microns thickness. (iii) Baseline assessment of T-cell receptor (TCR) rearrangement of TILs using next-gen sequencing technique requires 8 unstained slides at 10-micron thickness. After the initial analysis, tumor blocks from each participant will be stored at the site in MRFBC Tissue Bank for potential later investigation.

Approximately 25% of patients enrolled in this protocol, n=15 (10 patients from MCM cohort and 5 patients from ALM cohort) are anticipated to have on-treatment fresh biopsies from safely accessible location during weeks 6, 7 or 8 into treatment. Each on-treatment biopsy will be

evaluated for CD8+, PD-L1+, and Ki-67+ cells at the invasive margin as a predictive biomarker of response (ii) TCR rearrangement in response to a combined immune checkpoint inhibitor therapy.

